End of Study (primary completion)	Defined as when the last subject is assessed or received an intervention for the purposes of final collection of data for the primary endpoint at Month 6
End of Study (end of trial)	Defined as when the last subject is assessed or received an intervention for evaluation in the study, including survival assessments

Abbreviation or Term	Definition/Explanation
FAS	Full analysis set
FL	Follicular lymphoma
Healthcare Facility	Clinical trial site
HGBCL	High grade B-cell lymphoma
HLH	Hemophagocytic lymphohistiocytosis
IB	Investigator’s Brochure
ICF	Informed consent form
ICU	Intensive care unit
IP	Investigational product
IRB/IEC	Institutional Review Board/Independent Ethics Committee
IRRC	Independent Radiological Review Committee
IWG	International Working Group
KTE-C19/axicabtagene ciloleucel	Autologous T cells transduced with retroviral vector containing anti-CD19 CD28/CD3 zeta chimeric antigen receptor
LTFU	Long-term follow-up
LVEF	Left ventricular ejection fraction
mITT	Modified intent-to-treat
MMSE	Mini-Mental Status Exam
MRI	Magnetic resonance imaging
MSGV1	Murine stem cell virus-based vector
NaCl	Sodium chloride
NCI	National Cancer Institute
NHL	Non-Hodgkin lymphoma
ORR	Objective response rate
OS	Overall survival
PET-CT	Positron emission tomography–computed tomography
PBMC	Peripheral blood mononuclear cell
PMBCL	Primary mediastinal B-cell lymphoma
PD	Progressive disease
PR	Partial response
PRO	Patient Reported Outcome - Common Terminology Criteria for Adverse Events
RCR	Replication-competent retrovirus
SAE	Serious adverse event
scFv	Single chain variable fragment

Abbreviation or Term	Definition/Explanation
SD	Stable disease
SMS	Safety management study
SOA	Schedule of assessment
SUSAR	Suspected unexpected serious adverse reaction
Study Day 0	Defined as the first day that axicabtagene ciloleucel is administered to the subject
TEAEs	Treatment-emergent adverse event
TFL	Transformed follicular lymphoma
ULN	Upper limit of normal
VAS	Visual analogue scale

Study Schema

[figure not shown]

TABLE OF CONTENTS

CLINICAL STUDY PROTOCOL SYNOPSIS	3
Inclusion Criteria	4
Exclusion Criteria	5
1.1 Inclusion of Women and Minorities	6
2. OBJECTIVES	15
2.1 Study Design	15
2.2 Protocol Objectives	16
3. BACKGROUND	16
3.1 Disease Background and Rationale	16
3.2 Radiation Therapy for Refractory Lymphoma/Leukemia Following CAR T Cell Therapy	18
3.3 Correlative Studies Background	19
4. PARTICIPANT SELECTION	20

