4. PARTICIPANT SELECTION

All subjects must sign and date the IRB/IEC approved consent form before initiating any study specific procedures or activities that are not part of a subject's routine care. Refer to [Section 10](#) for details.

Each subject who enters the screening period will receive a unique subject identification (**ID**) number before any study specific procedures or activities are initiated. This number will be used to identify the subject throughout the study and must be used on all study documentation related to the subject. Furthermore, the subject identification number must remain constant throughout the entire clinical study, it must not be changed after enrollment or if the subject is rescreened or retreated.

4.1 Diagnosis and selection criteria: refractory hematologic malignancy following any CD19-targeted CAR T cell therapy

Inclusion Criteria

1. Biopsy-confirmed refractory disease within 30 to 90 days following any CD19-targeted CAR T cell therapy for a hematologic malignancy (these include relapsed or refractory large B-cell lymphoma after two or more lines of systemic therapy, including diffuse large B-cell lymphoma (DLBCL) not otherwise specified, primary mediastinal large B-cell lymphoma, high grade B-cell lymphoma, DLBCL arising from follicular lymphoma, and mantle cell lymphoma)

2. At least 1 measurable lesion according to the Lugano criteria¹. Lesions that have been previously irradiated will be considered measurable only if progression has been documented following completion of radiation therapy
3. Toxicities due to prior therapy must be stable and recovered to \leq Grade 1 (except for clinically non-significant toxicities such as alopecia) if there is concern for overlap of anticipated radiation-related toxicity and toxicity from prior therapy due to where the radiation therapy field is located.
4. Age 18 or older
5. Eastern Cooperative Oncology Group (ECOG) performance status of less than or equal to 2.
6. Females of childbearing potential must have a negative serum or urine pregnancy test (females who have undergone surgical sterilization or who have been postmenopausal for at least 2 years are not considered to be of childbearing potential)
7. Ability to understand and the willingness to sign a written informed consent document.

Exclusion Criteria

1. Any medical condition likely to interfere with assessment of safety or efficacy of RT

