7. ADVERSE EVENTS: LIST AND REPORTING REQUIREMENTS

7.1 Expected Toxicities

To date, the following important risks have been identified with axicel and tisacel: CRS, neurologic toxicities, infections, and cytopenias. Grading and management of these toxicities will be performed utilizing the recently released ASTCT CRS/ICANS grading system²¹. Please refer to the current product label for axicel, tisacel, lisocabtagene maraleucel, and brexucabtagene autoleucel for discussion of CRS and neurotoxicity (ICANS). Treatment with RT will occur after 30 day post-infusion period during which centers are FDA mandated to observe for peak toxicities. Additional information and management recommendations can also be found in appendix A. The following are important risks identified with radiation therapy but depend upon the target site for radiation therapy: dermatitis, pneumonitis, esophagitis, fatigue.

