7.4 Procedures for AE and SAE Collection and Reporting

7.4.1 Reporting of Adverse Events

The investigator is responsible for ensuring that all adverse events observed by the investigator or reported by the subject that occur from enrollment (ie, radiation therapy consultation) through 3 months after RT are monitored and reported. After 3 months, targeted adverse events including (eg, neurological, hematological, infections, autoimmune disorders, and secondary malignancies) will be monitored and reported for 6 months after treatment with axicel or tisacel or until disease progression, whichever occurs first.

The investigator must address the below for adverse events:

- Adverse event diagnosis or syndrome (if not known, signs or symptoms)
- Dates of onset and resolution
- Severity
- Assessment of relatedness to investigational product, lymphodepleting chemotherapy or study procedures
- Action taken

In reviewing adverse events, investigators must assess whether the adverse event is possibly related to 1) CAR T cell therapy product 2) RT, or 3) any protocol-required study procedure. The relationship is indicated by a yes or no response and entered into the CRF. A yes response should indicate that there is evidence to suggest a causal relationship between the study treatment or procedure and the adverse event. Additional relevant data with respect to describing the adverse event will be collected in the CRFs.

The investigator is responsible for reviewing laboratory test results and determining whether an abnormal value in an individual study subject represents a clinically significant change from the subject's baseline values. In general, abnormal laboratory findings without clinical significance (based on the Investigator's judgment) are not to be recorded as adverse events. However, abnormal laboratory findings that result in new or worsening clinical sequelae, require therapy or adjustment in current therapy are considered adverse events. Where applicable, clinical sequelae (not the laboratory abnormality) are to be recorded as the adverse event.

The investigator is expected to follow reported adverse events until stabilization or resolution. If a subject begins a new anticancer therapy, the adverse event reporting period for non-serious adverse events ends at the time the new treatment is started.

7.4.2 Reporting of Serious Adverse Events and Non-serious CRS events Grade ≥ 3

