9.7.5 Long-term Follow-up Period

All subjects who complete the study, and those who withdraw from the study after receiving RT for reasons other than death, will be asked to participate in the long-term follow-up portion of this study up to 12 months from CAR-T infusion, with a focus on long-term efficacy and safety. These patients will also have long-term follow-up as part of the FDA mandated CIBMTR CAR T cell therapy registry.

The following procedures will be completed for subjects who are enrolled at the time points of 6, 9, and 12 months following CAR-T infusion, as outlined in the SOA (Long-term Follow-up Period) Table 3:

- Physical exam
- CTCAE/PRO-CTCAE Surveys
- PET-CT/ Disease assessment at 6 and 12 months per standard of care
- Survival status
- Labs
 - CBC with differential
 - Cytokine levels
 - Lymphocyte subsets
 - Translational lab collection.
- Subsequent therapy for the treatment of NHL
- **Refer to Sections 8.4** for targeted adverse/serious adverse event reporting
 - Including neurological, hematological, infections, autoimmune disorders, and secondary malignancies
- Targeted concomitant medication documentation (for 12 months or until disease progression, whichever occurs first)
 - Including gammaglobulins, immunosuppressive drugs, anti-infectives, and vaccinations

Subjects may be contacted by telephone to confirm survival status and report targeted concomitant medication use.

If a subject progress in the LTFU phase, the subject will continue to be followed for survival status and subsequent therapy for the treatment of NHL. A translational lab sample and **serum (for cytokine evaluation)** should be collected at the time of progression as part of CAR T cell therapy protocol, prior to starting any subsequent anti-cancer therapy.

Should the subject fail to return to the clinic for a scheduled protocol specific visit, sites will need to make 2 attempts by a combination of telephone and mail to contact the subject. Sites must document both attempts to contact the subject. If a subject does not respond within 1 month after the second contact the subject will be considered lost to follow-up and no additional contact will be required.

As patients will be receiving commercial product, patients will also have long-term follow-up as part of FDA mandated CAR T cell therapy registry.

Table 2. Schedule of Assessments

Procedures	Screening	Enrollment & RT Planning	Radiotherapy		Post Radiotherapy Period			

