12.1 Study Endpoints

Primary Endpoint:

- Rate and severity of RT-related toxicity as per CTCAE v5.0 criteria during RT or within the first 30 days of completing RT.

Secondary Endpoints:

- **Duration of response (DOR):** Among subjects who experience an objective response, DOR is defined as the date of their first objective response (which is subsequently confirmed) to disease progression per Lugano criteria¹ or death regardless of cause. Subjects not meeting the criteria for progression or death by the analysis data cutoff date will be censored at their last evaluable disease assessment date and their response will be noted as ongoing.
- **Objective response rate (ORR) per IRRC:** ORR per IRRC is defined as the incidence of either a complete response or a partial response by Lugano criteria¹ as determined by the IRRC. All subjects that do not meet the criteria for an objective response by the analysis data cutoff date will be considered non-responders.
- **Progression-free Survival (PFS):** PFS is defined as the time from RT completion date to the date of disease progression per Lugano criteria¹ or death from any cause. Subjects not meeting the criteria for progression by the analysis data cutoff date will be censored at their last evaluable disease assessment date.

- **Overall survival (OS):** OS is defined as the time from RT completion to the date of death. Subjects who have not died by the analysis data cutoff date will be censored at their last contact date.

Exploratory Endpoints:

- Levels of anti-CD19 CAR T cells in blood
- Levels of cytokines in serum
- Incidence of anti-axicabtagene ciloleucel antibodies
- Investigation of potential biomarker development based on assessment of blood cells, tumor cells and the proposed actions of the investigational product.

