12.2 Sample Size, Accrual Rate and Study Duration

In terms of number of patients we anticipate to enroll, 53 patients underwent axicel or tisacel therapy at MGH within the past year. With a modest 30% refractory disease rate, 16 patients would have refractory disease and may be eligible for radiation therapy to achieve disease control. For the next one year, given the increasing rate of patients being referred for CAR T cell therapy, we expect that 80 patients are expected to undergo axicel or tisacel therapy – as such, **we modestly anticipate enrolling 20 patients who are candidates for RT on this study.** In terms of sample size calculation, with a 95% confidence level and a confidence interval of 10, with 0.3 (refractory disease rate) * 80 patients = 24 eligible in the population, the required sample size is 19 patients. It is noted that this is a **pilot** study, where the primary objective is assessing safety and toxicity, within the limits of what a pilot study can establish. Typically recommended ranges for pilot study sample sizes tend to range from 10 – 30. The number 20 is based primarily on how many patients can be accrued within a year and how many patients there is funding for. We are most concerned about Grade 4 or higher toxicity within RT field. Patients will have many different anatomic sites in terms of radiation treatment. Inherently, while a sample size calculation can be done as an exercise, the validity of it is highly questionable given the multiple anatomic sites to which patients may receive RT and no published data of patients who undergo RT following CAR T cell therapy. Results from this pilot study will be used to design a larger study, and for that, sample size can be computed based on what safety and

toxicity-related events are seen in the pilot study. Univariate descriptive statistics with t-tests will be used to analyze pre- and post-RT QOL and toxicity data.

All subjects will be followed for survival for up to approximately 15 years after the last subject receives CAR T cell therapy, with data collected through the CIBMTR data registry starting at Month 24.

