12.5 Reporting and Exclusions

The statistical reporting of the safety and efficacy endpoints will be compared to historical controls of patients with refractory disease following CAR T cell therapy who did not undergo RT. Subject incidence rates of axicel or tisacel-related adverse events, and ORRs will be summarized. DOR, PFS, and OS will also be summarized.

Analysis Subsets

Access to Individual Subject Treatment Assignments

This is a single arm, open-label study and subjects and investigators will be aware of treatment received. Data handling procedures for the the study will be devised to reduce potential sources of bias and maintain the validity and credibility of the study. These procedures will be outlined in the study statistical analysis plan and Trial Integrity Document.

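### Any CD19-targeted CAR T product is eligible, but the CAR-T adverse-event summary (12.5) and the late targeted-AE window (7.4.1) name only axicel or tisacel

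*Combined protocol and SAP*

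**What the plan says.** Eligibility is product-neutral. Section 4.1 requires "Biopsy-confirmed refractory disease within 30 to 90 days following any CD19-targeted CAR T cell therapy for a hematologic malignancy" and lists mantle cell lymphoma among the diagnoses; the synopsis criteria do the same. Section 7.1 refers to the labels of four products: axicel, tisacel, lisocabtagene maraleucel and brexucabtagene autoleucel.

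Two safety rules are product-specific:

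- Section 7.4.1 collects all adverse events to 3 months after RT. Beyond that, targeted events "will be monitored and reported for 6 months after treatment with axicel or tisacel or until disease progression, whichever occurs first".
- Section 12.5 states: "Subject incidence rates of axicel or tisacel-related adverse events, and ORRs will be summarized". The sentence just before it plans a comparison of safety and efficacy with historical controls who had refractory disease after CAR T therapy and no RT, without naming a product.

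Two further items name axicabtagene alone: the Study Glossary's Day 0 ("Defined as the first day that axicabtagene ciloleucel is administered to the subject") and an exploratory endpoint in 12.1 ("Incidence of anti-axicabtagene ciloleucel antibodies"), for which no denominator is set.

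**The concern.** The protocol foresees patients whom 12.5 and 7.4.1 do not mention. Section 3.2.1 describes patients eligible for commercial axicel or tisacel as having acute lymphoblastic leukemia or large B-cell lymphoma, while 4.1 also admits mantle cell lymphoma. On the protocol's own account, such a patient would have come from another product.

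The wording looks like an incomplete update. Section 12.2 says "we expect that 80 patients are expected to undergo axicel or tisacel therapy", while the synopsis gives the same 80 for all CD19-targeted CAR T therapy.

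At stake is the CAR-T-related event rate that the trial will report and set against history. If it covers only two products, it describes a narrower group than the one enrolled and than the one used as comparator, although attribution data exist for everyone. Section 12.2 intends the results to inform the design of a larger study.

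**Working it through.** The plan states no figure on this point, so there is none to reproduce. The check compares the rules and then does date arithmetic on the 7.4.1 window.

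**1. Which rules depend on product**

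| Rule | Product scope |
|---|---|
| 7.3: relationship of every AE to CAR T treatment | any |
| 7.4.1: all AEs to 3 months after RT; yes/no attribution to CAR T product, RT or procedure | any |
| 7.4.1: targeted AEs after that, to 6 months after CAR T | axicel or tisacel |
| 7.4.2: serious targeted AEs to 6 months after RT | any |
| 7.4.4: pause rule on Grade 4+ CAR-T-related AEs | any |
| Table 3: targeted AEs/SAEs at months 6, 9 and 12 from infusion; footnote 7 says 24 months | any |
| 12.4: all, serious, fatal, Grade 3+ and treatment-related AEs | any, but CAR T and RT not separated |
| 12.5: CAR-T-related AE rates | axicel or tisacel |

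Collection is almost entirely product-neutral. The one summary specific to CAR T is not.

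**2. Length of the product-limited part of 7.4.1**

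Inputs, in days:

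- C, from infusion to confirmed refractory disease: 30 to 90 (4.1).
- P, RT planning: 7 to 14 (9.7.2), taken to start on the day of confirmation.
- D, RT duration: not given; assumed 0 to 35.
- One month = 30.44 days, so 3 months = 91.3 and 6 months = 182.6.

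All-AE collection ends at C + P + D + 91.3. The 7.4.1 late window ends at 182.6. The remaining window is

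L = max(0, 182.6 − (C + P + D + 91.3)) = max(0, 91.3 − (C + P + D)).

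| C | Longest (P = 7, D = 0) | Shortest (P = 14, D = 35) |
|---|---|---|
| 30 | 91.3 − 37 = 54 | 91.3 − 79 = 12 |
| 60 | 91.3 − 67 = 24 | 91.3 − 109 < 0, so 0 |
| 90 | 91.3 − 97 < 0, so 0 | 0 |

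Progression can end the window sooner. Serious targeted events under 7.4.2 run to C + P + D + 182.6, at the earliest 37 + 182.6 = day 220, for any product. The part that depends on product therefore matters only for non-serious events.

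**3. Effect on the 12.5 rate**

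Section 12.5 gives no denominator. Let k of 20 patients have another product, with a patients having a CAR-T-related event among the 20 − k and b among the k. The all-product rate is (a + b)/20.

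- If only the numerator is restricted, the report shows a/20, a shortfall of b/20.
- If both are restricted, it shows a/(20 − k). This is above or below the all-product rate according to whether a/(20 − k) is above or below b/k.

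The documents give none of k, a or b. The precision cost under the second reading can be shown as a range. With zero events, the exact two-sided 95% upper limit is 1 − 0.025^(1/n):

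- n = 20: 16.8%.
- n = 18 (10% on other products, assumed): 18.5%.
- n = 10 (50% on other products, assumed): 30.8%.

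**4. Antibody endpoint**

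If all 20 patients form the denominator, everyone who did not receive axicabtagene, tisacel recipients included, counts as a negative. The incidence among axicabtagene recipients is then multiplied by (number of axicabtagene recipients)/20.

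**The case against.** The strongest reply is that this is stale product wording with little consequence. Every AE to 3 months after RT is recorded and attributed to the CAR T product whatever that product was; serious targeted events, the pause rule, the Table 3 visits and the 12.4 tables are also product-neutral. Most of this stands, and it rules out several stronger readings:

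- *CAR-T toxicity in other recipients is lost.* It is not; the rules in step 1 collect it.
- *Those patients have no late targeted-AE schedule.* Table 3 gives them one, counted from CAR-T infusion.
- *The reported rate is understated.* That would follow only if the numerator alone were restricted, and 12.5 does not say so.
- *Pregnancies after other products go unmonitored.* Section 7.4.3 also requires reporting of any pregnancy within 6 months of completing RT. As RT follows the 30-day post-infusion period, that window ends later than the axicel/tisacel one.
- *The glossary Day 0 removes patients.* It clashes with the RT Day 0 in Table 2, but visits are counted from RT start or from CAR-T infusion, so no data are lost.
- *Recipients of investigational products lack follow-up.* Section 9.7.5 says "As patients will be receiving commercial product, patients will also have long-term follow-up as part of FDA mandated CAR T cell therapy registry", and 3.2.1 does not say that the site's 30 investigational protocols are CD19-targeted or feed this trial.

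The reply does not cure 12.5. Section 12.4 reports treatment-related events without separating CAR T from RT, so no other planned output gives a CAR-T-related rate. Nor can Table 3 simply be taken to repair 7.4.1. Three late windows conflict: 6 months after CAR T (7.4.1), 6 months after RT for serious events (7.4.2) and 24 months (Table 3, footnote 7). Section 9.7.5 sends the reader for targeted events to an 8.4 that does not exist; the evident target is 7.4, where the restricted wording sits.

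**Conclusion.** The inconsistency is real and lies in operative text. Followed literally, 12.5 leaves eligible patients out of the only CAR-T-specific event rate although their attribution data are in hand, and 7.4.1 omits them from late reporting of non-serious targeted events. The second gap is small: at most about 54 days, 12 to 54 days for patients confirmed at day 30, and nothing at day 90. These figures assume RT of 0 to 35 days and planning that starts at confirmation.

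A reader might infer that the primary safety result is compromised. It is not: the primary endpoint is RT-related toxicity during RT and for 30 days afterwards, and no product wording touches it. The sample size is unaffected as well. The size and direction of any effect on the CAR-T rate cannot be stated without the product mix and a denominator. The point is worth correcting because the rule as written gives an incomplete summary and the correction is nearly free.

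**What to change.** - **12.5:** summarise adverse events related to the CD19-targeted CAR T product received, with all treated patients as the denominator.
- **7.4.1:** use the same product wording, and reconcile its late targeted-AE window with 7.4.2 and Table 3 footnote 7. Changing the product name alone would leave that conflict and a window that is empty for some patients.
- **12.1:** report the exploratory anti-axicabtagene antibody incidence among axicabtagene recipients only.

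The cost is a wording amendment. Attribution to the CAR T product is already recorded for every patient, and Table 3 already schedules late targeted-event collection for all products. The sponsor should accept that the CAR-T-related rate may look slightly less favourable once all products count.
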